5.7 Prior, Concomitant, and Excluded Therapies

Prior therapies (including over-the-counter medications) used to treat chronic pruritus of unknown origin within the prior 3 months, including those used during the screening period, will be recorded for each subject at the Baseline visit.

Concomitant therapies include any therapies (including over-the-counter medications and bland emollients) used by a subject from initiation of study drug treatment through the follow-up period. A record of all medications used will be maintained for each subject throughout the study. Reported information will include a description of the type of drug, treatment period, dosing regimen, the route of administration, and drug indication. The use of

any concomitant medication must relate to the subject's medical history or to an AE, except for vitamins/nutritional supplements, emollient use, and routine preventative immunizations.

All therapies that will be continued as concomitant therapies should be captured in source documents within 1 week of the Screening visit.

5.7.1 *Allowed Therapies*

Subjects using oral contraceptives, hormone-replacement therapy, or other maintenance therapies that are not Excluded Therapies ([Section 5.7.2](#)) may continue their use during the study.

Use of gentle cleansers and bland emollients (including those with urea) is encouraged for all subjects. If bland emollient use is elected, it must be initiated at least 3 weeks (21 days) prior to Baseline visit and continued throughout the treatment period.

Maintenance allergy immunotherapy will be allowed.

Treatment with non-systemic corticosteroids or antihistamines that do not involve skin application (e.g. inhaled, intranasal, ophthalmic, or intra-articular) will be allowed.

Leukotriene inhibitors will be allowed for treatment of conditions other than chronic pruritus of unknown origin (e.g. asthma).

5.7.2 *Excluded Therapies*

The following therapies and activities are excluded from 3 weeks prior to randomization through the treatment and follow-up periods:

- NK₁ receptor antagonists (other than study drug)
- Systemic or topical immunosuppressive/ immunomodulatory therapies (including but not limited to corticosteroids, PDE-4 inhibitors, cyclosporine, mycophenolate-mofetil, tacrolimus, pimecrolimus, calcipotriene, methotrexate, azathioprine, thalidomide, interferon-gamma, phototherapy). Build-up allergy immunotherapy will be excluded.
- Any medications that, in the investigator's and/or medical monitor's opinion, are suspected of having a causal or contributory role in the subject's pruritus.
- Biologic therapies (other than therapies such as insulins, vaccines)
- Strong CYP3A4 inhibitors (See [Appendix B](#))
- Use of an indoor tanning facility, or natural sun exposure resulting in significant tanning or sunburn
- Any investigational therapy

The following therapies and activities are excluded from 3 weeks prior to randomization through the treatment period. Use is discouraged, though permitted, in the follow-up period:

- Topical therapies or emollients with anti-pruritic properties (including but not limited to anti-histamines, menthol or menthol derivatives, polidocanol, camphor, pramoxine, cannabinoids, colloidal oatmeal baths, and capsaicin)
- Systemic therapies with recognized anti-pruritic properties (including but not limited to H1 antihistamines, doxepin, gabapentin, pregabalin, cannabinoids, kappa-opioid receptor agonists, and mu-opioid receptor antagonists)

Use of any excluded therapies (including those for the treatment of pruritus, or as rescue therapy) should be reported as soon as possible, and will be recorded as protocol deviations for subjects who receive them.

5.7.3 *Rescue Therapies*

The initiation of non-study drug therapy to treat worsening of pruritus is strongly discouraged throughout the treatment period. However, should rescue therapy be required for the safety and well-being of the subject, such use will be recorded and analyzed (see [Section 8.2](#)). The subject may remain on study drug, unless the rescue therapy is an NK₁ receptor antagonist, a systemic biologic therapy, a strong CYP3A4 inhibitor, an investigational therapy, or any therapy that may jeopardize the subject's safety if study drug is continued, in the investigator's and/or Sponsor's opinion.

5.8 Assignment to Treatment

5.8.1 *Randomization*

At the baseline visit eligible subjects will be randomized to receive serlopitant 5 mg or placebo in a 1:1 ratio. Stratified permuted block randomization will be used. Randomization will be stratified by the subject's reported WI-NRS score for the 1-week period prior to the Baseline visit (7 to < 8.5, 8.5 to 10), and by the subject's age at the Baseline visit (18 to < 50 years, ≥ 50 years).

Randomization of subjects < 50 years of age will be capped at 25% of the total randomized population. This cap may be increased up to 33% of the total randomized population at the Sponsor's discretion based on relative enrollment rates.

An IWRS will be used to perform the randomization.

5.8.2 *Blinding*

This study will be conducted as a double-blind study with the treatment assignment concealed from the subjects, the investigators and their staff, the Sponsor, and any designees of the Sponsor as required. The placebo will be formulated to be indistinguishable from the active study product. Study materials will be packaged and issued in a manner designed to

maintain the blind for subjects and all study personnel involved in the direction and execution of study procedures, study assessments, and collection of data. The randomization code for each subject will be available to the sites for use only in an emergency situation. For details of the procedure for unblinding of individual subjects in cases of emergency see [Section 7.6](#).

5.9 Treatment Compliance

Records of study drug used, dosages administered, and intervals between visits will be kept during the study. Subjects will be asked to return all partially used and empty bottles to the study site at each visit. The site staff will count and record the number of remaining tablets in each returned bottle. Study site staff will also regularly review eDiary-based study drug compliance records throughout the study. A subject who has deviated significantly from the once-daily dosing regimen will be counseled.

6 STUDY SCHEDULE AND ASSESSMENTS

When applicable, efficacy and safety instruments will be provided with instructions for administration, in study-specific manuals for site reference.

6.1 Efficacy Parameters

6.1.1 *Itch Numeric Rating Scale*

The Itch NRS is a validated, self-reported instrument for measurement of itch intensity. It uses a 24-hour recall period and asks subjects to rate the intensity of their itch on an 11-point scale ranging from 0 (no itch) to 10 (worst itch imaginable). Higher scores indicate greater itch intensity. The questionnaire is provided in [Appendix C](#).

During the study, WI-NRS assessments will be reported by the subject via eDiary. Subjects will record their WI-NRS scores once daily at approximately the same time each day (+/- 3 hours) throughout the screening, treatment, and follow-up periods, as outlined in [Appendix A](#). Subjects may be allowed to adjust the timing of eDiary completion within the first week of Screening as needed. Standardized training and instructions will be provided to all subjects prior to eDiary use.

6.1.2 *Itch Visual Analog Scale*

The Itch VAS is a validated, self-reported instrument for measurement of itch intensity. It uses a 24-hour recall period and asks subjects to rate the intensity of their worst itch on a 100-mm horizontal line ranging from 0 mm (no itch) to 100 mm (worst itch imaginable). Higher scores indicate greater itch intensity. The VAS measurement will be summarized in centimeters. Standardized paper questionnaires will be distributed to sites and, in order to ensure consistency, cannot be copied, printed, or faxed.

During the study, WI-VAS assessments will be reported by the subject via a paper form administered at study visits. Standardized training and instructions will be provided to all subjects prior to administration of the WI-VAS assessments.

6.1.3 *Static Patient Global Assessment of Itch Severity*

The Static Patient Global Assessment of Itch Severity (sPGA) is designed to assess overall itch severity. Each subject is asked to rate the severity of his/her itchiness in the past 7 days on a 5-point scale as none, mild, moderate, severe, and very severe. Higher scores indicate greater itch severity. The sPGA scores will be captured on paper according to the schedule in [Appendix A](#).

6.1.4 *Patient Global Impression of Change in Itch Severity*

The Patient Global Impression of Change in Itch Severity (PGIC) is a single item used to assess the change in overall itch severity since the baseline visit. Each subject will rate the change in his/her itch severity on a 7-point scale from (very much better) to (very much worse). PGIC scores will be captured on paper according to the schedule in [Appendix A](#).

6.1.5 *Epworth Sleepiness Scale*

The ESS is a QOL instrument intended to measure daytime sleepiness by use of a very short questionnaire (8 items each scored from 0–3). The ESS score can range from 0 to 24. Higher scores indicate greater daytime sleepiness. The questionnaire takes approximately 2 to 3 minutes to complete, and is provided in [Appendix D](#). The ESS questionnaire will be collected as outlined in [Appendix A](#).

6.2 Safety Parameters

Safety assessments will consist of monitoring and recording AEs and SAEs, vital signs, physical examinations, clinical laboratory assessments, ECGs, and other protocol-specified tests that are deemed critical to the safety evaluation of the study drug according to the schedule in [Appendix A](#).

6.2.1 *Vital Signs*

Vital signs will include measurements of heart rate, blood pressure, respiration rate, and temperature after the subject has been calmly resting (seated or supine) for a minimum of 5 minutes. Vital signs will be assessed according to the schedule in [Appendix A](#) and at unscheduled study visits when clinically indicated. On study visits when clinical laboratory tests are performed, assessment of vital signs should precede blood draw.

6.2.2 *Physical Examination*

Physical examinations, including height and weight measurements, will be performed according to the schedule in [Appendix A](#) and at unscheduled study visits when clinically indicated. A complete physical examination will be performed at the screening visit, while subsequent examinations will be abbreviated and targeted to changes in disease activity

and/or subjects' symptoms. If targeted breast examinations are to be performed in female subjects, please perform breast examination after blood draw for clinical laboratory tests.

6.2.3 Clinical Laboratory Assessments

Samples for clinical laboratory assessments will be collected according to the schedule in [Appendix A](#) and at unscheduled study visits when clinically indicated, and analyzed at a central laboratory unless otherwise specified.

Detailed instructions regarding sample collection, preparation, and shipment can be found in the laboratory manual. Laboratory assessments will include the following, and are ideally performed in the morning, particularly at visits with endocrine assessments (Screening, Week 10, and Follow-up):

- Hematology: hematocrit, hemoglobin, red blood cell count, red blood cell indices, platelets, white blood cell count, white blood cell differential (neutrophils, lymphocytes, monocytes, basophils, eosinophils)
- Chemistry: sodium, potassium, chloride, bicarbonate, glucose, blood urea nitrogen, creatinine, calcium, phosphorus, magnesium, albumin, uric acid, total protein, ALT, AST, alkaline phosphatase, total bilirubin, lactate dehydrogenase (LDH), lipid panel
- Iron studies: ferritin, serum iron
- Serology: hepatitis B and C serology, HIV
- Serum IgE
- Pregnancy testing: all females of childbearing potential will have a local urine pregnancy test performed. Positive or equivocal urine pregnancy test results will be confirmed by a serum pregnancy test analyzed at a central laboratory
- Endocrine: TSH, free T4, cortisol, corticotropin (adrenocorticotropic hormone, ACTH), prolactin
- Reproductive endocrinology (for all female subjects under 55 years of age at consent, who are not using hormonal contraception or other hormonal therapies at Screening): serum follicle-stimulating hormone (FSH), luteinizing hormone (LH), estradiol, progesterone, anti-Mullerian hormone (AMH)
- Optional study provided in lab test kits for use at Screening only: endomysial antibody with reflex to titer for subjects with signs or symptoms of dermatitis herpetiformis
- Additional optional studies deemed necessary by the investigator to rule out specific conditions associated with chronic pruritus based on a subject's history, physical examination, and/or screening labs may be performed; the investigator should discuss the need for such studies with the medical monitor during the Screening period.

- Standard cosyntropin stimulation testing should be performed on subjects with low cortisol level (i.e. < 3.0 mcg/dL); the investigator should discuss low cortisol (and relevant low corticotropin) results with the medical monitor.

6.2.4 *Electrocardiogram*

A standard 12-lead ECG will be performed after the subject has been calmly resting in a supine position for a minimum of 5 minutes before obtaining the ECG. ECGs should precede measurement of vital signs and blood draw for clinical laboratory tests and will be performed according to the schedule in [Appendix A](#) and at unscheduled study visits when clinically indicated. ECGs will be read centrally. The ECG machine and detailed instructions will be provided by the ECG vendor.

[figure not shown]

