1.3 Serlopitant

1.3.1 Serlopitant Background and Nonclinical Summary

Serlopitant is a small molecule, highly selective NK₁-R antagonist that is administered orally and metabolized by cytochrome P-450 3A4 (CYP3A4), with a plasma half-life of 45–86 hours. It binds with high affinity to the human NK₁-R with a dissociation constant (K_d) of 46 pM; displacing SP binding with a half-maximal inhibition concentration (IC₅₀) of 61 pM. Serlopitant is a potent functional antagonist of SP-induced inositol phosphate generation.

Serlopitant has been extensively studied in animal toxicology studies, including chronic toxicology and carcinogenicity studies. In non-clinical chronic toxicology studies in rats, mice and dogs, treatment related findings of potential clinical significance included increased salivation, decreased body weight gain and food consumption, slight changes in hematology and serum biochemistry parameters, mild increases in liver weight and mild histomorphologic changes. The histomorphologic changes were seen only in rats (not in dogs or mice) and included: very slight ovarian interstitial cell hypertrophy, mammary gland and uterine atrophy; decreased corpora lutea; increased histiocytes in lung and mesenteric lymph nodes; slight skeletal and cardiac muscle degeneration; slight increased hematopoiesis in bone marrow; and slight to moderate vacuolation in kidney tubules. These nonclinical findings occurred at systemic exposures exceeding those anticipated to provide efficacy of serlopitant for pruritus indications in humans (1 to 5 mg tablet daily). No cardiac lesions have

been observed in dog toxicity studies up to 9 months in duration nor in a 3-month mouse range-finding study and 2-year mouse carcinogenicity study at exposure higher than the lowest level which caused cardiotoxicity in rats. The no observed adverse effect level (NOAEL) in rats for histomorphological changes in the reproductive tract, mammary gland and bone marrow provides a 2.5-fold margin for the maximum-targeted exposure (5 mg tablet daily). The rat NOAEL for histomorphological changes in muscle and kidney provides a 5-fold margin for the maximum-targeted exposure (5 mg tablet daily).

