6.5.1 Screening Period

Informed consent will occur prior to any protocol-mandated procedures, including the stopping of any excluded therapies. This may occur prior to the Screening visit.

The screening period for all subjects is 3 weeks to allow for washout of any excluded therapies. Subjects will have a telephone contact approximately 2 weeks prior to the scheduled Baseline visit to review inclusion and exclusion criteria, check on any

procedure-related adverse events, and remind them to complete the eDiary as previously instructed at the Screening visit.

Screening procedures may be deferred with the medical monitor's agreement should more than 3 weeks be required (e.g. to wash out of certain excluded therapies or to treat their underlying condition). Screening procedures may be repeated with the medical monitor's agreement.

The subject may be rescreened once with the medical monitor's agreement.

6.5.2 *Screening Visit*

The following screening procedures are to be performed at the Screening visit, preferably in the order shown below:

- Obtain written informed consent prior to any protocol-mandated procedures, including the stopping of any excluded therapies
- Collect demographic information (sex, date of birth, race, ethnicity)
- Ask subject to complete the WI-NRS scale on paper
- Register Screening visit into the IWRS
- Obtain ECG
- Obtain vital signs
- Review subject's medical history (including pruritus treatments in the past 3 months and current medications)
 - Record only significant/relevant medical history, to include the onset date of itch (as specifically as known)
 - Review for the presence of any underlying conditions that may exclude the subject from study eligibility
 - Female subjects should be queried regarding their childbearing potential and history of, or current, breast masses or abnormal discharge, and history of mammography (if applicable), and history of abnormal vaginal bleeding or discharge
- Perform complete physical examination (including height and weight)
- Perform a urine pregnancy test for females of childbearing potential (with positive or equivocal results confirmed by a serum pregnancy test)
- Draw blood for clinical laboratory tests (morning blood sampling due to Endocrine assessments)
 - Reproductive endocrine labs for females under 55 years of age at consent who are not using hormonal contraception or other hormonal therapies at Screening

- Endocrine
- Hematology
- Chemistry
- Serology
- Serum IgE

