6.5.4 Baseline Visit

The Baseline visit occurs 3 weeks (+3 days) after the screening visit. Eligibility must be confirmed prior to randomization. At the Baseline visit, the following procedures and assessments are to be performed, preferably in the order shown below:

- Ask the subject to complete the WI-VAS, ESS, and sPGA questionnaires
- Assess and record any changes in the subject's concomitant medications

- Assess and record any changes in the subject's medical history
 - Female subjects should be queried regarding history of, or current, breast masses or abnormal discharge, and history of mammography (if applicable), and history of abnormal vaginal bleeding or discharge
- Assess AEs and record SAEs caused by protocol-mandated interventions
- Obtain vital signs
- Perform a urine pregnancy test for females of childbearing potential and confirm the subject has a negative urine pregnancy test result prior to randomization (with positive or equivocal results confirmed by a serum pregnancy test)
- Confirm subject's eligibility based on the inclusion/exclusion criteria (to include review of eDiary compliance for eligibility)
- Randomize subject in IWRS if eligibility confirmed
- Perform targeted physical examination, including weight
- Dispense 1 bottle of study drug; subjects will take loading dose of 3 tablets while on site
- Assess and record any post-dose AEs and SAEs
- Confirm next scheduled visit

6.5.5 *Week 1 Telephone Contact Visit*

The Week 1 visit is a telephone visit that occurs 7 days (\pm 3 days) after the Baseline visit. At the Week 1 visit, the following procedures and assessments are to be performed:

- Assess and record any changes in the subject's concomitant medications
- Assess and record any AEs and SAEs
- Review eDiary for compliance, re-train subject as needed
- Review study drug compliance with re-training as required
- Confirm next scheduled visit

6.5.6 *Week 2 Visit*

The Week 2 visit occurs 14 days (-3/+1 days) after the Baseline visit. At the Week 2 visit, the following procedures and assessments are to be performed:

- Ask the subject to complete the WI-VAS, ESS, sPGA, and PGIC questionnaires

- Assess and record any changes in the subject's concomitant medications
- Female subjects should be queried for presence of new breast masses or abnormal discharge, and abnormal vaginal bleeding or discharge
- Obtain vital signs
- Assess and record any AEs and SAEs
- Review eDiary for compliance, re-train subject as needed

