3.5.2 Clinical Laboratory Evaluations

Clinical laboratory results will be summarized by type of laboratory assessment (hematology, chemistry, endocrine), timepoint, and treatment. Summary statistics for actual values and changes from baseline will be tabulated by analysis window. Shifts from baseline clinical laboratory values based upon the normal range will be tabulated for each post baseline sample timepoint. These tables will utilize the normal ranges provided for the individual sample.

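### Neither document requires menstrual-cycle timing at the reproductive-hormone draws, so pooled change-from-baseline and shift tables would say little about luteal function in cycling women

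*Protocol*

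**What the plan says.** Protocol 6.2.3 defines a reproductive panel, "serum follicle-stimulating hormone (FSH), luteinizing hormone (LH), estradiol, progesterone, anti-Mullerian hormone (AMH"), "for all female subjects under 55 years of age at consent, who are not using hormonal contraception or other hormonal therapies at Screening". The visit lists in Protocol 6.5.2, 6.5.10 and 6.5.11 place it at Screening, Week 10 and Follow-up. The one timing condition is that laboratory assessments "are ideally performed in the morning, particularly at visits with endocrine assessments (Screening, Week 10, and Follow-up").

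The questions put to women concern other matters. At Screening (Protocol 6.5.2): "Female subjects should be queried regarding their childbearing potential and history of, or current, breast masses" or abnormal discharge, mammography and abnormal vaginal bleeding. At Baseline (Protocol 6.5.4) they again include "history of abnormal vaginal bleeding or discharge". No section of either document asks for the last menstrual period, cycle day or phase. Further collection detail is deferred: "Detailed instructions regarding sample collection, preparation, and shipment can be found in the laboratory manual".

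On analysis, Protocol 8.9.2 tabulates actual values, changes from baseline, out-of-range values and shifts for laboratory results, with no exception for this panel. SAP 3.5.2 does the same for hematology, chemistry and endocrine results: "Shifts from baseline clinical laboratory values based upon the normal range will be tabulated for each post baseline sample timepoint". It uses the range supplied with each sample and gives no rule for cycle phase or menopausal status. SAP 3.2 sets baseline as the last value before dosing, which for these hormones is the Screening sample.

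**The concern.** In a woman with a natural cycle, progesterone and estradiol, and to a lesser degree LH and FSH, vary with the day of the cycle. Draws fixed to study visits fall on arbitrary cycle days. A change or a range shift can then appear without any drug effect, and a real effect on the luteal phase is visible only in women who happen to be luteal when sampled on treatment.

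The panel has a specific purpose to serve. Protocol 1.3.1 reports "very slight ovarian interstitial cell hypertrophy, mammary gland and uterine atrophy; decreased corpora lutea" in rats, with a 2.5-fold exposure margin at 5 mg daily for the reproductive-tract changes. Progesterone is the product of the corpus luteum. If the planned tables cannot separate phase from drug, an unremarkable table would be read as reassurance that it does not provide.

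**Working it through.** The plan gives no figure for the hormone analyses, so there is none to reproduce. Its only power statement concerns the primary endpoint, and the responder rates there are redacted.

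**1. Visit gaps (Protocol 6.5.4, 6.5.10, 6.5.11), for women who complete treatment.**
- Screening to Week 10: 21 + 70 = 91 days, or up to 24 + 73 = 97 with the windows.
- Screening to Follow-up: 91 + 35 = 126 days, or up to 97 + 42 = 139.
- For an exact 28-day cycle at nominal visits: 91 - 84 = 7 and 126 - 112 = 14 days out of phase.

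**2. Phase changes with no drug effect.** Assumptions: cycle length uniform over 25-35 days, Screening on a random cycle day, the last 14 days luteal, visit windows used uniformly. By simulation, 48% of cycling women are in a different phase at Week 10 than at Screening, and 44% at Follow-up. With an exact 28-day cycle and nominal visits the shares are 50% and 100%.

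**3. How much of the change is phase.** Share = V / (V + 2s²), where V is the variance of the phase-driven log change and s the within-woman log SD. Hormone profiles and s are assumptions; the cycle is 28 days and the gap 91-97 days.

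| Hormone | Low end | High end |
|---|---|---|
| Progesterone | 1.70² / (1.70² + 2×0.5²) = 85% | 2.66² / (2.66² + 2×0.3²) = 98% |
| Estradiol | 0.71² / (0.71² + 2×0.5²) = 50% | 0.98² / (0.98² + 2×0.2²) = 92% |
| LH | 0.58² / (0.58² + 2×0.5²) = 40% | 0.97² / (0.97² + 2×0.2²) = 92% |
| FSH | 0.37² / (0.37² + 2×0.5²) = 22% | 0.68² / (0.68² + 2×0.2²) = 85% |

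**4. How many cycling women.** The under-50 cap (Protocol 5.8.1) is 25% × 200 = 50, or 33% × 200 = 66 subjects of both sexes, that is 25-33 per arm. Assuming 50-70% women, of whom 40-80% cycle and use no hormones: 25 × 0.5 × 0.4 = 5 to 33 × 0.7 × 0.8 ≈ 18 per arm. Women aged 50-54 may add a few.

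**5. Power of change from baseline.** Assumptions: progesterone 0.5 ng/mL follicular and 10 ng/mL luteal, log SDs of 0.3-0.5, drug halves luteal values, two-sided 5% test. By simulation for 8-20 women per arm, power is about 7-16% on the raw scale and 5-8% on the log scale.

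An analytic check agrees. A halving is ln 2 = 0.693 on the log scale. Only about half the women are luteal at Week 10, so the mean effect is about 0.347. With an SD of change of 2.0, the number needed per arm for 80% power is 2 × (1.96 + 0.84)² × 2.0² / 0.347² ≈ 523. With an SD of 1.5 it is about 295.

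**6. What the last-period date alone recovers.** With a 14-day luteal phase, ovulation falls between day 25 - 14 = 11 and day 35 - 14 = 21, so days since the last period misplace some women. Comparing Week 10 values in women classed as luteal by a day 14-21 cut-off gives about 12-16%, 20-28% and 26-51% power at 8, 12 and 20 per arm. Repeat runs moved these by up to about three points.

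**The case against.** The case against has several sound parts.

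- **What the SAP plans.** SAP 3.5.2 names only hematology, chemistry and endocrine. Protocol 6.2.3 lists endocrine and reproductive endocrinology separately, although SAP Table 1 puts them in one row. That this panel gets change and shift tables therefore rests on Protocol 8.9.2, or on a broad reading of endocrine. If the panel is not covered, the SAP has no planned summary for it, which also needs settling.
- **What cannot be seen.** The laboratory manual, the eCRF and the ranges attached to each sample are not available. A reader might infer that cycle timing is never collected. The documents support only that neither of them requires it and that no planned table uses it.
- **Bias.** A reader might infer a distorted arm comparison. Randomization balances phase on average, so the loss is in precision and dilution.
- **Reach.** A reader might infer that all four hormones mainly track phase, or that every woman is in the opposite phase at Follow-up. The first fails for LH and FSH under the noisier assumptions, and does not apply to postmenopausal women in the panel. The second needs an exact 28-day cycle and unused windows.
- **Importance.** Protocol 1.3.1 says the changes were seen only in rats and above the exposure anticipated for efficacy. AMH is also measured, and abnormal bleeding is asked about at the on-site visits. The panel is not the only safeguard.
- **Power.** Safety is descriptive (SAP 2.9), no hormone test is planned, and actual values by visit are tabulated as well. The power figures are a gauge of information, not a description of a planned test.

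None of this makes pooled change and shift tables informative about luteal function in cycling women.

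**Conclusion.** The concern holds in a limited form. The protocol and SAP do not require cycle timing at the reproductive-hormone draws, and the pooled tables planned in Protocol 8.9.2 (and in SAP 3.5.2, if endocrine includes this panel) would be largely uninformative about a luteal effect in women with natural cycles. Roughly 48% and 44% change phase by Week 10 and Follow-up without any drug effect, and change from baseline has about 5-16% power for a halving of luteal progesterone. These sizes rest on assumed cycle lengths, luteal length, hormone levels and variability, none of which the documents give. The finding is firm for progesterone, usual for estradiol and assumption-dependent for LH and FSH.

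A reader might also infer that recording the last period would make this a well-powered comparison. It would not: that date classifies phase imperfectly, and the age cap leaves about 5-18 cycling women per arm under the stated assumptions. The gain is tables that can be interpreted. The change is worth making because it is cheap and cycle dates are hard to recover reliably later.

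**What to change.** **Data collection.** At each reproductive-endocrine draw, record on the eCRF menopausal status and the first day of the last menstrual period. Add usual cycle length or, where obtainable at the next contact, the start of the next period. No contact is scheduled after Follow-up, so that draw would rely on usual cycle length.

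**SAP 3.5.2.** State that the reproductive panel is summarized. For premenopausal women, replace the pooled change and shift tables for FSH, LH, estradiol and progesterone with descriptive actual values by arm and phase (follicular, luteal, unknown). Use phase-specific ranges where the laboratory supplies them. Keep the planned tables for AMH and for postmenopausal women.

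**Cost.** A few eCRF fields at three existing visits, a question at a later contact, and one SAP table specification; no extra sample or visit. The downside is small cells and an unknown row for irregular cycles, so the tables should be labelled descriptive.
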